In a prospective randomised trial the "ProTwin Trial"⁸ 813 women with twin pregnancies at a gestational age of 16 weeks to 20 weeks were randomised to either

pessary treatment or expectant management. Subgroup analysis of women with a shortened cervix below the 25 percentile (=38 mm) showed for the pessary group a significant 6-fold decrease in perinatal mortality and a reduction of severe morbidity. This demonstrates that an early screening followed by an early intervention is essential for patients at-risk. A secondary analysis “*per protocol*” of the ProTwinTrial revealed that the success of pessary treatment was mostly dependent on the correct placement and the duration of the therapy ⁹.

A further prospective-randomised trial by Goya et. al ¹⁰ also proved a significant reduction of the preterm delivery rate in twin pregnancies with cervical shortening (<25 mm, 20-24 weeks of gestation) after placement of a pessary compared to expectant management; the reduction in mortality was less pronounced than in the ProTwin Trial. A new case-control-trial by Fox et al. ¹¹ showed a decrease in early preterm birth before 32 weeks of gestation (4.8% vs. 28.6%, P=.05), a considerable prolongation of pregnancy (65.2 d. vs. 52.1 d, P=.025) and a reduced neonatal morbidity (9.5% vs. 34.9%, P=.04) in twin pregnancies after pessary therapy.

A secondary analysis of the ProTwin Trial indicated a higher survival rate without neurodevelopmental disability in the long-term outcome 3 years after pessary treatment (92.4 vs. 73.8%, p=0.006) compared to expectant management ¹².

A prospective, randomised controlled trial by Nikolaides ¹³ and a cohort study by Monfrance ¹⁴ in twin pregnancies with short cervix showed no significant effect of the pessary therapy compared to expectant management.

Up to now there is just one Cochrane review available concerning pessary therapy and the authors concluded that in spite of the positive effects seen that more trials should be conducted ¹⁵.

2.2. Description of the study population.

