 - Preterm birth before 30 weeks: rate of delivery before 29+6 weeks
 - Preterm birth before 28 weeks: rate of delivery before 27+6 weeks
 - Birth weight: median weight (g) of the newborns at birth
 - Fetal or neonatal death: rate of intrauterine demise or neonatal death during the first 24 hours
 - Neonatal morbidity: rate of major adverse neonatal outcomes before discharge from the hospital
 - Intraventricular Haemorrhage (IVH): grades III-IV
 - Retinopathy of prematurity
 - Respiratory Distress Syndrome (RDS): grades II-IV,
 - Need for ventilation > 72 h
 - Necrotising enterocolitis
 - Proven or suspected sepsis, antibiotics (>5 days)
 - Need (Duration in days) for neonatal special care (NICU)
 - Harm from intervention
- Mother:
 - Maternal death
 - Significant maternal adverse events (rate):
 - Heavy bleeding: bleeding that requires a medical intervention
 - Cervical tear: cervical rupture due to the pessary placement
 - Uterine rupture: rupture of the uterus due to contractions or surgery
 - Physical or psychological intolerance to pessary: discomfort or pain due to the pessary that makes daily life uncomfortable (number of cases)
 - Rupture of membranes before 32 weeks: rate of–rupture of amniotic membranes before 31+6 weeks

[figure not shown]
- Infection/inflammation
- Hospitalisation for threatened preterm labour before 32 weeks: requirement of hospitalisation due to preterm contractions that need medical treatment to try to stop them before 31+6 weeks (rate)
 - Mean hospital stay duration: number of days of admittance at the hospital
 - Use of tocolytic treatment: Type of tocolytic, days of treatment, dose

4.2. Description of the trial design.

Open Multicentre International Collaborative Randomized Controlled Trial, in parallel groups, based on intention-to-treat analysis comparing the placement of a prophylactic cervical pessary with usual management in twin pregnancies with shortened cervix ≤ 25 percentile

4.3. Flowchart.

4.4. Description of the medical device and the treatment regimen.

The cervical pessary is a vaginal device (silicone ring) that is used to treat pregnant women for preventing spontaneous preterm birth. This device can be easily placed around the uterine cervix without pain (see annex I).

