A descriptive analysis by preterm birth will be carried out calculating means and medians for quantitative variables and proportions with 95% confidence intervals for categorical variables. In general, statistical comparisons with the pessary arm and the control arms or other group comparisons for primary and secondary outcomes will be performed with stratified tests as well as comparisons in the gestation subgroups. Events will be analysed for each twin and for single children assuming appropriate random effect regression models. Further subgroup analyses regarding the cervical length will be performed (e.g. CL 15 to 25mm and below 15mm). All tests, see also examples in the synopsis, will be two-sided using a significance level of $\alpha=0.05$.

For the primary endpoint we expect to have a drop out rate of up to 25% due to the long follow-up time (3 years) of the study; but we do not expect to have lost data for the secondary endpoints because for these parameters the study has a short follow-up time till time to birth only.

An interim analysis shall be conducted on key safety parameters after birth of 300 twins: the following safety endpoints will be assessed by a one-sided test with $\alpha=1\%$

- on level of the neonates: rate of preterm birth, time to birth, birth weight, death, neonatal morbidity, harm of intervention
- and on the maternal level: rate of hospitalisation for threatened preterm labour < 32 weeks, rate of PRoM <32 weeks, rate of infection / inflammation, rate of physical or psychological intolerance to pessary, rate of SAR/SAE, death.

The trial will be terminated as negative if a disadvantage for the pessary-treatment can be found in one of these tests. To guarantee a high safety level the significance level is chosen more conservatively than in a Bonferroni correction.

All analysis will be carried out with SPSS® version 19.0 or later (IBM Company SPSS Inc. Headquarters, Chicago, Illinois, USA) and R version 3.2.3 or later (R Foundation for Statistical Computing, Vienna, Austria).

Primary Outcome	Statistical Test
Children`s Long-Term Survival without Neuro-developmental Disability (3-Years-follow up)	Cochran-Mantel-Haenszel-Test, using 3 strata according to WoG
Secondary Outcome	Statistical Test
Birth before 34 Weeks of Gestation	Cochran-Mantel-Haenszel-Test, Chi-Quadrat Test
Time to Birth	Cox-Regression
Birthweight	van Elteren Test, Wilcoxon-Mann-Whitney Test
Fetal / Neonatal Death	Cochran-Mantel-Haenszel-Test, Chi-Quadrat Test

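### Neonatal morbidity leaves out death and has no stated denominator, so better survival can look like a morbidity disadvantage in the secondary comparison and in a stand-alone interim stopping test

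*Combined protocol and SAP*

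**What the plan says.** Section 4.1.2 keeps death and morbidity apart. Death is "Fetal or neonatal death: rate of intrauterine demise or neonatal death during the first 24 hours". Morbidity is "Neonatal morbidity: rate of major adverse neonatal outcomes before discharge from the hospital", followed by diagnoses such as severe intraventricular haemorrhage, retinopathy, respiratory distress syndrome, ventilation beyond 72 hours, necrotising enterocolitis and sepsis. None of these is death. Neither Section 4.1.2 nor the table of tests in Section 9.1 says whether the denominator is all fetuses, live births or survivors.

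Section 9.1 adds an interim look: "An interim analysis shall be conducted on key safety parameters after birth of 300 twins". Each endpoint is tested one-sided at 1%. The neonatal list reads "on level of the neonates: rate of preterm birth, time to birth, birth weight, death, neonatal morbidity, harm of intervention", so death and morbidity are separate tests. The consequence is mandatory: "The trial will be terminated as negative if a disadvantage for the pessary-treatment can be found in one of these tests". The external committee in Section 9.3 is mentioned only for maternal death.

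Section 2.1 reports for the short-cervix subgroup of an earlier trial "a significant 6-fold decrease in perinatal mortality and a reduction of severe morbidity".

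**The concern.** Recruitment starts at 16 weeks, and part of the rationale is a large fall in perinatal mortality. A fetus lost in utero, or an infant who dies very early, usually cannot acquire the later diagnoses. A child who would have died in the control arm but survives with a listed morbidity in the pessary arm therefore adds a morbidity event to the pessary arm with nothing to set against it. The groups compared are selected by survival, which the device is meant to change.

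Two results are exposed. The secondary morbidity comparison can mislead. At the interim, a favourable death result cannot offset an unfavourable morbidity result, because one adverse test is enough. That also sits badly with the primary outcome, in which survival is part of success.

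**Working it through.** The documents give no stopping probability for the interim, so there is no figure of the plan's to reproduce first. What follows is a sensitivity calculation.

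**Inputs from the documents.** Six-fold mortality ratio (Section 2.1). One-sided 1% test, critical value 2.326 (Section 9.1). Interim size: 300 twins may mean 300 children (150 per arm) or 300 twin pregnancies (600 children, 300 per arm). The only morbidity rates given are 9.5% vs 34.9%, favouring the pessary, from the cited case-control study (Section 2.1).

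**Assumptions.** Control and pessary death rates d_c and d_p; morbidity s in control survivors; morbidity m = 50 to 70% in infants saved by the pessary; infants independent.

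**Direction.** With survivors as denominator, and no effect on other infants:

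pessary morbidity = [(1 − d_c)·s + (d_c − d_p)·m] / (1 − d_p)

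This is a weighted average of s and m, so it exceeds s only if m > s. If deaths are instead counted as morbidity-free, the denominator is 1 and any morbidity in saved infants raises the pessary rate.

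**One case in full.** d_c = 12%, d_p = 2%, s = 10%, m = 70%: (0.88 × 0.10 + 0.10 × 0.70)/0.98 = 0.158/0.98 = 16.1%, against 10.0%. With 300 fetuses per arm there are 264 and 294 survivors. The pooled rate is 13.2%, the null standard error 0.0287 and the alternative standard error 0.0283. Stopping probability = Φ[(0.0612 − 2.326 × 0.0287)/0.0283] = Φ(−0.20) = 42%. In the same case deaths favour the pessary with z = 0.10/√(0.07 × 0.93 × 2/300) = 4.8.

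**Range.** Same formula, m from 50 to 70%. Where other infants benefit, s is multiplied by 0.8 in the pessary arm.

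| Deaths, control vs pessary | Control morbidity s | Fall in other infants | Survivor morbidity, control vs pessary | Stop, 150/arm | Stop, 300/arm | Stop if deaths count as morbidity-free (150; 300) |
|---|---|---|---|---|---|---|
| 12% vs 2% | 10% | none | 10.0% vs 14.1–16.1% | 10–20% | 19–42% | 17–31%; 35–61% |
| 8% vs 1.5% | 10% | none | 10.0% vs 12.6–14.0% | 5–10% | 9–19% | 8–14%; 15–28% |
| 12% vs 2% | 20% | none | 20.0% vs 23.1–25.1% | 4–9% | 7–19% | 11–20%; 21–41% |
| 12% vs 2% | 20% | 20% | 20.0% vs 19.5–21.5% | 0.7–2.2% | 0.7–2.9% | 2–6%; 3–11% |
| 12% vs 2% | 34.9% | none | 34.9% vs 36.4–38.5% | 2–4% | 3–7% | 8–15%; 15–30% |
| 12% vs 2% | 34.9% | 20% | 34.9% vs 30.2–32.2% | 0.3% or less | 0.1% or less | 0.6–1.5%; 0.4–1.8% |

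With no true difference the test stops with probability 1%. A variance inflation of 1.5 for twin clustering (assumed) lowers the first row to 7–13% and 13–28%. At the cited 9.5% vs 34.9% the probability is practically nil.

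**Deaths that already carry a listed morbidity.** If a fraction f of deaths had a listed diagnosis first, the per-fetus rates in the first row become 0.088 + 0.12f and 0.088 + 0.10m + 0.02f. For f = 25% the stopping probability is 5–23% over both interim sizes; for f = 50% it is 1–5%.

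**Composite of death or morbidity, first row.** Control 0.12 + 0.088 = 20.8%; pessary 0.02 + 0.138 to 0.158 = 15.8 to 17.8%. The stopping probability is about 0.1% or less.

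**What the composite would miss.** Suppose survivor morbidity truly doubles, 10% to 20%, with the same deaths. The existing test stops with probability about 50–55% (150 per arm) or 84–87% (300 per arm); the lower figures apply after removing deaths from the denominator. The composite is 20.8% vs 0.02 + 0.98 × 0.20 = 21.6%, and stops with about 2%.

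**The case against.** The strongest reply is that Section 2.1 expects morbidity to fall together with mortality, and the only morbidity rates it cites strongly favour the pessary. The higher probabilities come from an unsourced 10% baseline and no benefit to other infants. The 12% death rate is also high against the trial's own planning. A pessary event rate of 8% and an odds ratio of 2.29 give a control rate of 16.6% per pregnancy for death or disability (odds 2.29 × 0.08/0.92 = 0.199). With independent infants, 12% mortality alone gives 1 − 0.88² = 22.6% of pregnancies with a death, and 8% gives 15.4%. All this stands, and it rules out any single headline figure. It does not remove the point. Section 2.1 also reports a smaller mortality effect in a second trial and two studies with no significant effect, so a parallel fall in morbidity cannot be taken for granted by a mandatory rule.

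A reader might infer that the bias always runs against the arm with better survival. It does not. With survivors as denominator it needs saved infants to be sicker than other survivors, and a loss near 20 weeks that becomes a late-preterm birth could carry little morbidity. Infants who develop a listed diagnosis and then die also still count as events.

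A reader might also infer that the composite should replace the interim morbidity test. The doubling example shows why not: a mortality gain could mask real morbidity harm. Testing death and morbidity separately for safety is defensible. The weakness is that the results are never weighed together.

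**Conclusion.** The concern holds in conditional form. Death is outside the morbidity endpoint, the denominator is open, and the morbidity test alone is enough to stop the trial. If the pessary saves infants who are sicker than other survivors, the comparison is biased against it, and the trial could be declared negative while deaths clearly favour the pessary.

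The documents supply only the mortality ratio, the test level and the interim count; every death and morbidity rate in the range is an assumption, apart from the cited 34.9%. Across those assumptions the chance of stopping on this test runs from under 1% to about 20 to 40%, and higher if deaths count as morbidity-free. The documents do not show that such a stop is likely. The secondary comparison has the same selection problem whatever happens at the interim, and there the repair is cheap.

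**What to change.** **Secondary comparison (Sections 4.1.2 and 9.1).** Analyse fetal or neonatal death, or any listed major morbidity, before discharge, with all fetuses alive at randomisation as the denominator. The random-effect models already planned for single children can handle the pairing of twins. Show death and each morbidity alongside, and state the denominator for each.

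**Data capture.** Record deaths to discharge, not only to 24 hours. As defined now, a death after 24 hours without a listed morbidity counts in neither endpoint.

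**Interim (Section 9.1).** Keep the separate death and morbidity tests and report the composite next to them. Reword the rule so that a morbidity disadvantage is read together with mortality before the trial is declared negative, and name who does that reading.

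**Cost.** Protocol wording and one extension of death recording; the morbidity items are already planned outcomes. The downside is that the composite mixes death with lesser morbidity, which is why the components must be shown and why it should not replace the safety test.

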This database will be supervised and coordinated by PD [name], Bürgerhospital Frankfurt/M. (Webmaster).

4.8. Identification of data to be collected in the case report files (CRF) that should be considered as data source.

Data will be collected in E-CRF, provided by >[name] Wissenschaft, Berlin< on study software "Castor".

4.9. Definition of what is considered to be the end of the study.

The study will be finished after the 3 year-follow up examination concerning neurodevelopmental disabilities, which will be conducted on the surviving children of the participating patients.

5. Selection and withdrawal of subjects

5.1. Inclusion criteria.

- Dichorionic diamnionic twin pregnancy with
- 16-28 weeks of gestation
- Minimal age of 18 years
- Informed consent signature

5.2. Exclusion criteria.

- Monochorionic twin pregnancy
- Major fetal abnormalities (requiring surgery or leading to infant death or severe handicap)
- Cerclage prior to randomisation
- Uterine malformation
- Placenta previa totalis
- Active vaginal bleeding at the moment of randomization
- Spontaneous rupture of membranes at the time of randomization
- Silicone allergy

- Current participation in other RCT
- Painful regular uterine contractions

5.3. Withdrawal criteria.

If a participant may voluntarily withdraw from treatment or if it is necessary to remove the pessary due to the conditions described before, the patients will be followed as usual until delivery (intention-to-treat analysis).

The death of one twin is not an exclusion criterion for the pessary placement.

The replacement of patients is not applicable in this trial.

5.4. Rescue treatment criteria.

If the cervical length decreases later on during the pregnancy, the management of the pregnancy in each centre will be the usual.

In case of secondary cervical shortening in the follow-up period pessary treatment may be offered as a rescue treatment up to 32+0 weeks of gestation.

Cervical cerclage or progesterone are generally not indicated in twin pregnancies.

6. Treatment of Subjects

6.1. Treatments to be administered.

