Neonatal Morbidity	Cochran-Mantel-Haenszel-Test, Chi-Quadrat Test
Need for Hospitalization (mother)	Cochran-Mantel-Haenszel-Test, Chi-Quadrat Test
Days of Hospitalization (mother)	van Elteren Test, Wilcoxon-Mann-Whitney Test
Maternal Adverse Events	Cochran-Mantel-Haenszel-Test, Chi-Quadrat Test
Pessary Intolerance	Cochran-Mantel-Haenszel-Test, Chi-Quadrat Test
Vaginal Infections	Cochran-Mantel-Haenszel-Test, Chi-Quadrat Test

9.2. Expected number of subjects to be included.

For sample size calculation, we account for the stratified design and assume three equally large gestation groups. For the pessary group, we assume a combined event rate of at least 8% for the primary outcome and for the comparison of the pessary group with the control group we assume an odds ratio of 2.29. This odds ratio correspond to the lower bound of a one-sided confidence interval for the event rate given in van't Hooft (ProTwin Trial¹²). To reach a power of at least 80%, we have to evaluate at least 500 patients, 250 in the pessary group and 250 in the control group. To account for a drop out rate of 25%, overall n=672 pregnant women will be recruited.

9.3. Criteria for termination of the trial.

A non-justified case of maternal death (temporary stop until complete evaluation of the case by an external committee).

9.4. Selection of subjects to be included in each analysis.

The analysis will include all the subjects that have been randomised.

10. Direct Access to Data Source

Direct access will be granted to the authorized monitor, host institution and the regulatory authorities to permit trial-related monitoring, audits and inspections.

11. Quality and Control Assurance

Main investigator and collaborators: In order to ensure the Quality of the data they will provide instructions and training to the sites involved in the trial; review the CRF data; and detail of any other steps taken to ensure quality of research.

The main investigator will sign the study protocol and the “investigator’s commitment; he will apply for the Ethics Committee and the Director’s approval; and he will review the final report of the study.

The collaborators will assess patient’s eligibility, they will inform the patients and ask for the informed consent; and they will be responsible of the CRF and obtaining and registering all data.

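### Cervical tear counts only when attributed to the pessary, so this component is not comparable between arms and the maternal adverse-event test can be biased in either direction

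*Combined protocol and SAP*

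**What the plan says.** Section 4.1.2 (maternal secondary outcomes) gives the rate of significant maternal adverse events and defines three components:

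- Heavy bleeding is defined by the need for medical treatment.
- The tear component reads: "Cervical tear: cervical rupture due to the pessary placement".
- For uterine rupture, the causes named are contractions and surgery.

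The first and third can be met in either arm without reference to the device. Only the second names the pessary as a required cause.

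The table of tests in 9.1 has a row "Maternal Adverse Events", to be tested by Cochran-Mantel-Haenszel and chi-square. The text of 9.1 describes group comparisons as pessary against control and adds: "All tests, see also examples in the synopsis, will be two-sided using a significance level of" 0.05.

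Three other provisions bear on the point.

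- Section 4.2 describes the design as "Open Multicentre International Collaborative Randomized Controlled Trial, in parallel groups, based on intention-to-treat analysis", so whoever attributes a tear knows the arm.
- Section 5.4 states: "In case of secondary cervical shortening in the follow-up period pessary treatment may be offered as a rescue treatment up to 32+0 weeks of gestation". It does not limit this to one arm.
- Section 8.3 has all adverse events entered on the CRF, whether or not they are attributed to treatment, together with an assessment of relatedness.

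**The concern.** A between-arm test of an event rate needs an event that can be counted on the same terms in both arms. Here a tear in a woman who never had a pessary falls outside the definition, whatever happened to her cervix. A tear in a woman with a pessary is in or out according to an unblinded opinion about cause. Counting therefore follows treatment received and attribution rather than randomised arm, which sits badly with the intention-to-treat framework of 4.2 and 9.4.

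Pessary intolerance, listed nearby, is a different case because it has no meaning without a pessary. A cervical tear can occur without one, for example at delivery, and only the wording removes it. The wording also leaves open whether placement means the insertion or the whole time in situ, so sites could code the same tear differently.

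At stake is the maternal safety comparison. It could report harm that is not there, or report less harm than there is.

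**Working it through.** **The plan's own figures.** No rate, difference or power is stated for maternal adverse events, so there is no figure to reproduce for this outcome. The sample size in 9.2 does reproduce. An event rate of 8% and odds ratio 2.29 imply odds of 0.08/0.92 × 2.29 = 0.199, a control rate of 16.6%. The CMH normal approximation with continuity correction then needs 502 women for 80% power (plan: 500). Dropout gives 500/0.75 = 667 (plan: 672). Nothing below changes these figures.

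**Inputs.**
- Women per arm: 672/2 = 336 (9.2, equal allocation). Section 9.1 expects no lost data for secondary endpoints.
- Two-sided α = 0.05 (9.1).
- Tear rate: not in the documents; assumed 1% to 3%.
- Rate of the other components together: not in the documents; assumed 2% to 10%.
- I read the composite as the three components above, because intolerance and vaginal infection have their own rows in the table of tests.

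**Step 1: direction.** Let *t* be the background tear rate (equal in both arms), *c* the excess caused by the pessary, *a* the share of background tears in the pessary arm blamed on the device, and *s* the share of caused tears recognised as such. Leave rescue pessaries in controls aside.

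- True risk difference: (*t* + *c*) − *t* = *c*
- Recorded risk difference: *a·t* + *s·c* − 0
- Bias: *a·t* − (1 − *s*)·*c*

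| Case | Bias |
|---|---|
| Perfect attribution: *a* = 0, *s* = 1 | 0 |
| *t* = 1%, *c* = 0, *a* = 1 | +1.0 point (against the pessary) |
| *t* = 1%, *c* = 0, *a* = 0.5 | +0.5 point (against the pessary) |
| *c* = 1 point, *a* = 0, *s* = 0.5 | −0.5 point (in its favour) |

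The sign depends on *a* and *s*, which the wording does not fix.

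**Step 2: tears tested alone, 336 per arm.**

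| Tears, pessary v control | Chi-square p (uncorrected) | Fisher p |
|---|---|---|
| 3 v 0 | 0.083 | 0.249 |
| 4 v 0 | 0.045 | 0.124 |
| 5 v 0 | 0.025 | 0.062 |
| 6 v 0 | 0.014 | 0.031 |

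Expected counts at 4 v 0 are only 2 per arm, so the uncorrected chi-square is unreliable there. At a true rate of 1%, 336 × 0.01 = 3.4 tears are expected per arm.

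**Step 3: the composite.** Add the same number of other events to each arm (uncorrected chi-square).

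| Other events per arm | 4 extra in pessary arm | 6 extra in pessary arm |
|---|---|---|
| 3 (about 1%) | 7 v 3: p=0.20 | 9 v 3: p=0.08 |
| 7 (about 2%) | 11 v 7: p=0.34 | 13 v 7: p=0.17 |
| 17 (about 5%) | 21 v 17: p=0.50 | 23 v 17: p=0.33 |

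**Step 4: chance of a false signal against the pessary in the composite.** With *c* = 0 and other events at rate *b*, the pessary rate is *b* + *a·t* and the control rate is *b*. The chance is Φ((*d* − 1.96·s₀)/s₁), where *d* = *a·t* and s₀, s₁ are the pooled and unpooled standard errors. For *b* = 5%, *t* = 1%, *a* = 1: *d* = 0.01, s₀ = √(2 × 0.055 × 0.945/336) = 0.0176, s₁ = 0.0176, giving Φ(−1.39) = 8.2%. Over *b* = 2–10% and *t* = 1–3%:

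- *a* = 0: 2.5%, the nominal one-sided level
- *a* = 0.5: 4.0% to 22.0%
- *a* = 1: 6.2% to 56.2%

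The top of each range pairs the highest tear rate with the lowest rate of other events.

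**The case against.** The strongest reply is that the definition drops non-pessary tears in both arms. If attribution is right, what remains is exactly the excess the device causes, which is a legitimate safety quantity. That is correct, and Step 1 shows it. It needs attribution to be right, however, and for tears the plan sets neither criteria nor blinded adjudication. It would also miss any effect of the pessary on background tears.

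Second, control tears are not lost, because 8.3 puts every adverse event on the CRF with relatedness. This stands, and it makes the repair cheap. It does not bring those tears into the outcome that 9.1 tests.

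Third, a control woman given a rescue pessary under 5.4 can have a qualifying tear. This also stands: the exclusion covers control women who receive no pessary, not every control woman.

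Fourth, attributing every delivery tear to the pessary is a worst case, particularly as the device is to be removed at 37+0 weeks or earlier. So the *a* = 1 results are an upper bound for given rates, not an expectation.

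A reader might infer two stronger things. One is that the test is biased against the pessary. The documents do not support that, since the direction depends on how investigators attribute. The other is that a control count near zero stops the comparison from showing a true excess. It does not: 6 v 0 would register.

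**Conclusion.** The point holds in limited form. As defined, the cervical tear component cannot be met by a control woman without a pessary and depends on unblinded attribution in the pessary arm, so it is not comparable between arms although a between-arm test is planned. The comparison can lean either way, and the risk difference is unbiased only if attribution is perfect and the pessary leaves background tears unchanged.

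The size cannot be stated, because neither the tear rate nor the rates of the other components are given. Under the assumed rates the effect ranges from none to substantial. In the composite, a handful of attributed tears would usually not reach significance alone. The 4 v 0 result for tears alone should not carry the argument, since it is significant only by the uncorrected chi-square.

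The consequence is confined to a secondary safety outcome. The primary analysis and sample size are untouched, and cervical tear is not named among the interim stopping endpoints in 9.1. It is still worth correcting, because the defect is plain and the repair small.

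**What to change.** In 4.1.2, drop the causal phrase and define the component as: *cervical rupture, regardless of cause, from randomisation to the end of delivery, in both arms*. Keep the word rupture. Widening it to any laceration would bring in minor delivery tears and lower the severity threshold of an outcome meant for significant events.

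Run the planned CMH and chi-square tests on this cause-neutral definition, by randomised arm. Report relatedness to the device, already recorded under 8.3, as a separate descriptive item.

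The cost is one changed definition and a check that the CRF prompts for cervical rupture in both arms. The targets of 500 evaluable and 672 recruited women do not change. The downside is that some delivery tears unrelated to the pessary will enter the count and add noise.
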